### 3.2 Evobrutinib

Evobrutinib (also known as M2951) is a novel inhibitor of Bruton's tyrosine kinase (BTK). Ibrutinib, the only approved molecule in this class, is used in the treatment of hematological malignancies. Several BTK inhibitors have been evaluated in preclinical models of RA, with some of these advancing to clinical development for treatment of RA ([Akinleye 2013](#), [Norman 2016](#), [Whang 2014](#)). Evobrutinib is being developed for the treatment of RA due to the known role of B cells and autoantibodies in RA. As inhibition of BTK has been shown to inhibit key B cell functions (eg, antigen presentation, proliferation, differentiation and cytokine production), and has also been shown to inhibit signaling via autoantibody/antigen engagement of the Fc receptor on non-B cells—all factors felt to contribute to RA disease biology—blockade of BTK is expected to provide clinical benefit to patients with RA. The expectation that BTK inhibition will be beneficial in RA is supported by recently reported data showing clinical efficacy in a small, early clinical trial of another BTK inhibitor, CC-292 ([Kivitz 2016](#)). As BTK inhibition is a different mechanism of action than currently available treatments for RA, the expectation is that treatment with

## Evobrutinib

### Phase IIb in Rheumatoid Arthritis MS200527-0060

---

evobrutinib will help patients that are not responsive to current therapies. Additionally, as evobrutinib is a highly selective BTK inhibitor, it may have a more favorable safety profile than ibrutinib.

A large, stylized logo consisting of the letters 'C', 'C', and 'I' in a bright red color. The 'C's are thick and rounded, and the 'I' is a simple vertical bar. The logo is centered at the top of a large black rectangular area that occupies most of the page.

Refer to the Investigator's Brochure (IB) for further information about the nonclinical and clinical programs and Guidance for the Investigator.

This clinical trial will be conducted in compliance with the clinical trial protocol, ICH GCP, the Japanese ministerial ordinance on GCP (for Japan only), and any additional applicable regulatory requirements.

## Evobrutinib

### Phase IIb in Rheumatoid Arthritis MS200527-0060

[figure not shown]
---

Based on the available nonclinical and clinical data to date, the conduct of the trial specified in this protocol is considered justifiable.

#### 3.4 Risk/Benefit

No identified risks or new potential risks have emerged from the completed Studies EMR200527-001 or MS200527-0019 in healthy volunteers or SLE Study EMR200527-002. No new safety signals have been confirmed from ongoing Study MS200527-0081 as of an IDMC data review meeting on 24 October 2017.

Important potential risks to subjects are based on nonclinical safety data of evobrutinib and clinical data on adverse drug effects associated with compounds of a similar pharmacological class. They include infection, leukopenia, thrombocytopenia, hemorrhage, gastrointestinal intolerance, renal toxicity, hepatocellular injury, atrial fibrillation, and embryo-fetal toxicity. The potential risk of infection relates to the immunomodulatory actions of evobrutinib. Women of childbearing potential participating in clinical studies with evobrutinib must agree to adhere to the use of highly effective contraception as specified in the clinical study protocol. CCI

Risk minimization measures routinely implemented in early phase clinical trials, including exclusion criteria for hematological cytopenias and stopping rules based on grade changes in specific laboratory parameters, are considered adequate for planned clinical trials in patients with autoimmune diseases. No additional risk minimization measures are proposed.

## Evobrutinib

### Phase IIb in Rheumatoid Arthritis MS200527-0060

---

Taking the above information into account, benefit-risk considerations support the proposed clinical trial of evobrutinib in patients with RA.

For the Japanese population, a Phase I trial (MS200527-0017) has been conducted to evaluate safety, pharmacokinetics (PK), and pharmacodynamics (PD) of evobrutinib as a bridging trial between Japanese and non-Japanese healthy subjects.

Refer to the Investigator's Brochure for more details of each trial.

This clinical trial will be conducted in compliance with the clinical trial protocol, ICH GCP, the Japanese ministerial ordinance on GCP (for Japan only), and any additional applicable regulatory requirements.

## 4 Trial Objectives

### 4.1 Primary Objective

The primary objective is:

- To evaluate the efficacy and dose response of 12 weeks of treatment with evobrutinib compared with placebo in subjects with rheumatoid arthritis (RA) with inadequate response to methotrexate (MTX-IR) on stable MTX therapy by assessment of the signs and symptoms of RA, as measured by American College of Rheumatology (ACR) 20% (ACR20) response assessed using high-sensitivity C-reactive protein (hsCRP) at Week 12.

### 4.2 Key Secondary Objective

The key secondary objectives are:

- To further evaluate the efficacy and dose response of 12 weeks of treatment with evobrutinib in MTX-IR subjects with RA on stable MTX therapy by assessment of the signs and symptoms of RA, as measured by DAS28-hsCRP low disease activity (DAS28 < 3.2) rate at Week 12
- To further evaluate the efficacy of 12 weeks of treatment with evobrutinib compared to placebo in MTX-IR subjects with RA on stable MTX therapy by assessment of the signs and symptoms of RA, as measured by DAS28-hsCRP remission (DAS28 < 2.6) rate at Week 12
- To further evaluate the efficacy and dose response of 12 weeks of treatment with evobrutinib in MTX-IR subjects with RA on stable MTX therapy by assessment of the signs and symptoms of RA, as measured by ACR50 and ACR70 at Week 12
- To evaluate the safety of evobrutinib in MTX-IR subjects with RA on stable MTX therapy.

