For the primary and key secondary efficacy analyses, ACR20 (ACR50/ACR70) response rate, the estimate of the odds ratio (OR), together with the associated 2-sided 95% CI and p-value, comparing each evobrutinib dose group to placebo, is based on a logistic regression model for the odds of ACR20 (ACR50/ACR70) response, with evobrutinib dose group or placebo as a factor and adjustment for covariates based on randomization strata (region, MRI-substudy participation).

The dose response will be assessed via a modeling approach as an additional supportive analysis.

Analysis of the change from Baseline scores of the MRI data will be performed on the appropriate analysis sets (eg, MRI analysis set for the RAMRIS scores) using a mixed-effect model for repeated measures, with treatment arm as factors, and randomization strata, and Baseline as covariates.

Analyses of all other secondary endpoints will be exploratory in nature.

Safety data will be listed and summarized using descriptive statistics.

CCI [REDACTED]

[REDACTED]

[REDACTED]

[REDACTED]

[REDACTED]

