#### 5.2.3.2.2 Other Secondary Endpoints

##### 5.2.3.2.2.1 Efficacy Endpoints

**ACR Hybrid** - The ACR hybrid score was developed to provide a quasi-continuous score that can detect smaller changes between treatments than the categorical ACR20/50/70 scores by combining the continuous score of the mean improvement in the core set measures combining the ACR20, ACR50, and ACR70 scores with the mean percent change from Baseline in all 7 ACR response core set components (Felson 2007, American College of Rheumatology Clinical Trial Priorities and Design Conference 2010, van Vollenhoven 2011). ACR hybrid, along with the DAS28, is recommended by the FDA regulatory guidance as a way to support dose-response assessment. It is calculated according to Table 6 (Felson 2007).

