## **8.5.2 Analysis of Primary Endpoint**

### **8.5.2.1 Efficacy Endpoints**

The primary analysis of ACR20 at Week 12 will be based on the mITT analysis set using Last Observation Carried Forward for imputation of missing values of each ACR component. A subject will be considered as a nonresponder if the subject discontinues prior to Week 12.

The estimate of the odds ratio (OR), together with the associated 2-sided 95% CI and p-value, comparing each evobrutinib dose group to placebo, will be provided based on a logistic regression model for the odds of ACR20 response, with evobrutinib dose group or placebo as a factor and adjustment for covariates based on randomization strata (region, MRI-substudy participation). In order to further characterize the dose-response, the proportion of ACR20 response at Week 12 will also be presented for each treatment group, along with the difference in ACR20 response proportion between evobrutinib and placebo, and the 95% CI for the difference. Details will be provided in the SAP.

The dose response will also be assessed via a modeling approach as additional supportive analyses. Details will be provided in the SAP.

Additional sensitivity analyses will be performed to assess the robustness of the primary missing data imputation method and will be described in detail in the SAP.

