## **8.5.3 Analysis of Secondary Endpoints**

### **8.5.3.1 Key Secondary Efficacy Endpoints**

Analyses of all key secondary efficacy endpoints will be performed using the same approach as the ACR20, based on the mITT analysis set.

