**Table 15 : Analysis of the Key Secondary Endpoints at Week 12**

Endpoints	Analysis Set	Analysis method	Description	Missing data handling

 
• DAS28-hsCRP < 3.2
 
• DAS28-hsCRP < 2.6
 
• ACR50
 
• ACR70
 
	
 
• mITT set
 
	Primary analysis: Stratified MN for $\Delta$	
 
• Presentation of response rate for each treatment group, <math>\Delta</math> in response rate compared to placebo, 2-sided 95% CI of <math>\Delta</math>, nominal p-value
 
• Summary Stats over time
 
	LOCF-NR*
	
 
• mITT set
 
	Descriptive statistics	Number and percentage of subjects with response status (Yes/No/Missing) over time	As observed

\* LOCF-NR: post-baseline last observation carried forward. Patients who discontinued from treatment are considered as non-responders

## 14.2.2 Other Secondary Endpoints at Week 12

The following secondary endpoints, defined in Appendix 18.1, will be presented on mITT analysis set:

- Achieving ACR EULAR Boolean remission
- Achieving CDAI score  $\leq 2.8$  (CDAI remission)
- Achieving SDAI score  $\leq 3.3$  (SDAI remission)
- EULAR Responder Index (based on DAS-hsCRP)
- ACR hybrid scores computed using hsCRP
- Change from Baseline in DAS28-hsCRP
- Change from Baseline in CDAI and SDAI
- Changes and percentage changes from Baseline of individual components of the ACR Core Set
- ESR (mm/Hr)

These endpoints will be analyzed according to Table 16.

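### The protocol sets dose response as an objective for DAS28-hsCRP < 3.2, ACR50 and ACR70, but the visible SAP plans no formal dose-response analysis for them and does not declare the departure.

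*Protocol*

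**What the plan says.** - **Objectives.** Protocol 4.2 gives the DAS28-hsCRP < 3.2 objective as "To further evaluate the efficacy and dose response of 12 weeks of treatment with evobrutinib in MTX-IR subjects with RA on stable MTX therapy". The same opening is used for the objective "as measured by ACR50 and ACR70 at Week 12". The DAS28-hsCRP < 2.6 objective asks only for efficacy against placebo and does not mention dose response. SAP Table 1 repeats all of this and points to SAP Section 14.2.
- **Protocol method.** Section 8.5.3.1: "Analyses of all key secondary efficacy endpoints will be performed using the same approach as the ACR20, based on the mITT analysis set". For ACR20, Section 8.5.2.1 says "The dose response will also be assessed via a modeling approach as additional supportive analyses". In the Synopsis, directly after a paragraph that covers ACR20, ACR50 and ACR70 together, comes "The dose response will be assessed via a modeling approach as an additional supportive analysis".
- **SAP method.** In SAP 14.1, Table 13 lists the Cochran-Armitage trend test (supportive analysis no. 5) and MCP-Mod (no. 6), both for ACR20. For the key secondary endpoints, the method entry in Table 15 reads "Primary analysis: Stratified MN for" followed by the symbol for the difference. It comes with response rates per arm, 95% CIs, nominal p-values and summaries over time, and a second row gives observed-case counts.
- **Declared changes.** The visible text of SAP Section 7 covers the Japanese consistency analysis, the open-label extension, the MRI analysis set and the MRI covariate. It does not mention dose response for the key secondary endpoints.

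**The concern.** Protocol 4.2 separates dose response from comparison with placebo: three endpoints get both and one gets only the second. SAP Table 15 treats all four identically, so the distinction is lost between the two documents. SAP 14.2.1 also refers to a supportive analysis of these endpoints on the mITT set, but Table 15 does not define one.

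The trial is meant to inform a Phase III dose. Three separate tests against placebo do not test for a dose response. A nominally significant result at one dose and a non-significant one at another is not evidence that the two doses differ, nor does it describe a curve. A reader who looks for the dose-response result on ACR50, ACR70 or low disease activity would have to form an impression from four rates. If an analysis were added after unblinding, it would have to be labelled post hoc.

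**Working it through.** **1. Objective against plan**

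| Endpoint | Dose response in Protocol 4.2 | Protocol method | Visible SAP analysis across doses |
|---|---|---|---|
| ACR20 (primary) | yes (4.1) | 8.5.2.1, with modelling | Cochran-Armitage, MCP-Mod |
| DAS28-hsCRP < 3.2 | yes | as ACR20 | none |
| ACR50 | yes | as ACR20 | none |
| ACR70 | yes | as ACR20 | none |
| DAS28-hsCRP < 2.6 | no | as ACR20 | none |

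For the three named endpoints the plan yields 3 endpoints × 3 doses = 9 nominal comparisons and no test or model across doses.

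**2. What a trend test would add.** The sample-size statement concerns ACR20 only. With 80 per arm and α = 0.05/3, power is 0.787 to 0.797 for 25 points and 0.929 to 0.940 for 30 points (placebo rates 30% to 45%). This agrees with the stated 80% and is slightly above the stated 90%. The documents give no rates for the other endpoints, so the following are assumptions: placebo 15% (or 12%), maximum effect 12 points, 90 per arm (non-responder imputation keeps discontinued subjects in the mITT set), dose scores 0/25/75/100 as in SAP 14.1, nominal two-sided 0.05.

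Formula for the trend test, with centred scores s = −50, −25, 25, 50 (sum of squares 6,250):

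power ≈ Φ[(n Σ p·s − 1.96 √V0) / √V1], where V0 = n·p̄(1−p̄)·Σs² and V1 = n·Σ p(1−p)s².

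Linear rates 15/18/24/27%:
- n Σ p·s = 90 × 7.5 = 675
- V0 = 90 × 0.21 × 0.79 × 6,250 = 93,319, root 305.5
- V1 = 90 × 1,017.75 = 91,598, root 302.7
- power ≈ Φ[(675 − 598.7)/302.7] = Φ(0.25) ≈ 0.60

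Top dose against placebo on the same rates: pooled standard error √(2 × 0.21 × 0.79/90) = 0.0607 and unpooled √(0.3246/90) = 0.0601, so power ≈ Φ[(0.12 − 0.1190)/0.0601] ≈ 0.51.

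The other shapes use the SAP Table 14 parameters, scaled to a 12-point maximum. Results are from simulation, 40,000 runs per row. The pairwise column is the dose with the largest effect.

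| Shape | Rates, % | Trend | Pairwise | Same shape, placebo 12%: trend / pairwise |
|---|---|---|---|---|
| Linear | 15/18/24/27 | 0.60 | 0.51 | 0.65 / 0.56 |
| Emax | 15/22.4/26.2/27 | 0.52 | 0.51 | 0.57 / 0.56 |
| Quadratic | 15/21.7/27/25.6 | 0.48 | 0.51 | 0.53 / 0.56 |
| Logistic | 15/15/23.9/27 | 0.70 | 0.51 | 0.75 / 0.56 |
| Plateau (15-point effect) | 15/30/30/30 | 0.54 | 0.68 | not run |

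The trend test gains for linear and logistic shapes, is level for Emax, and loses for quadratic and plateau shapes. Power for MCP-Mod itself was not computed. Its candidate set includes Emax and quadratic curves, which is the reason to plan it beside the trend test.

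**3. Which ACR20 settings carry over.** The Table 14 parameters are standardised shapes and can be reused. The dose targets cannot: SAP 14.1 sets the minimum effective dose at a 20-point difference and further targets at 25, 30 and 35 points. With a true maximum effect of 12 points, as assumed above, 12 < 20, so the true curve reaches none of the targets.

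**The case against.** **The objectives are not left unanswered.** A reader might infer that these objectives cannot be answered at all. The documents do not support that. Protocol 8.5.2.1 itself says "In order to further characterize the dose-response, the proportion of ACR20 response at Week 12 will also be presented for each treatment group", together with differences from placebo, and SAP 14.1 repeats this for the stratified difference. Table 15 plans that same display for the key secondary endpoints. SAP 14.1 also plans a bar chart, by arm, of the cumulative proportion reaching each ACR cut-off, with lines at 50% and 70%. This stands: a descriptive reading is planned. But for ACR20 both documents set modelling beside that display, and Protocol 8.5.3.1 extends the whole approach.

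**Redaction.** SAP Section 7 contains a redacted block, and Section 16 and parts of Sections 14.2.5 and 18 are blacked out. SAP Section 9 mentions a modelling and simulation analysis by the sponsor whose scope is not visible. This stands too: absence can be stated only for the visible text.

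**Supportive status.** All secondary analyses are supportive and nominal (SAP 14.2), and the ACR20 modelling is itself supportive. That limits the weight of the point. It does not remove the mismatch with a stated objective.

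**ACR hybrid and change in DAS28.** Protocol 5.2.3.2.2.1 says "ACR hybrid, along with the DAS28, is recommended by the FDA regulatory guidance as a way to support dose-response assessment", and a reader might infer that these scores also need dose-response modelling. No visible objective requires it: Protocol 4.3 asks only for efficacy, and Section 8.5.3.3 calls the other efficacy endpoints exploratory. The sentence is background, so this extension is not part of the point.

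**Conclusion.** The point holds as a gap in the analysis plan. Three key secondary objectives name dose response, the protocol commits to the ACR20 approach for them, and the visible SAP neither carries this out nor declares the change. As written, these objectives are met only descriptively. The primary inference, its error control and the data collected are unaffected.

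The case for acting rests on answering a stated objective as the protocol promised, not on a general gain in power. A gain appears only for some monotone shapes (0.60 against 0.51 if linear) and disappears or reverses for others. These figures depend on the assumed rates, on 90 per arm, and on treating 50 mg BID as 100 mg daily, as the SAP does.

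**What to change.** - In SAP Table 15, for DAS28-hsCRP < 3.2, ACR50 and ACR70, add the Cochran-Armitage trend test, and the MCP-Mod contrast test and model fit with the Table 14 candidate set. Both would be nominal and supportive, on the mITT set with LOCF-NR. This would also define the supportive analysis that SAP 14.2.1 mentions.
- Do not reuse the ACR20 targets of 20, 25, 30 and 35 points. Either pre-specify targets for each endpoint, or report only the test and the fitted curve.
- Record any remaining departure from Protocol 8.5.3.1 in SAP Section 7. If the sponsor prefers a descriptive reading for these endpoints, say so there.

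The cost is SAP wording, adaptation of code already planned for ACR20, and a decision on targets, with no new subjects or data. The downside is a few more unadjusted p-values, and a trend test that can miss a plateau or a downturn, so it should be read beside the model fit and the rates per arm.

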### 4.3 Other Secondary Objectives

The other secondary objectives are:

- To further evaluate the efficacy of evobrutinib on the signs and symptoms of RA with inadequate response to MTX
- To evaluate the effect of evobrutinib on joint structures and inflammation, at Weeks 4 and 12 in the MRI substudy, as assessed by magnetic resonance imaging (MRI)
- To evaluate the effect of evobrutinib on physical function in RA subjects
- To evaluate the effect of evobrutinib on subject-reported health-related quality of life (HRQoL)
- To evaluate the effect of evobrutinib on subject-reported fatigue (using Functional Assessment of Chronic Illness Therapy [FACIT]-Fatigue).

A large, stylized logo consisting of the letters 'C', 'C', and 'I' in a bold, red, sans-serif font. The 'C's are open on the right side, and the 'I' is a solid vertical bar. The logo is centered on a solid black rectangular background.

## 5 Investigational Plan

### 5.1 Overall Trial Design and Plan

This is a Phase IIb, multicenter, international, randomized, double-blind, placebo-controlled parallel-arm trial, designed to determine the efficacy, dose response, and safety of evobrutinib in subjects with RA, and to consider a dose to take forward into Phase III development. Approximately 360 total subjects 18 to 75 years of age with RA planned to be randomized (to obtain 320 evaluable subjects). The study includes a Japanese cohort (approximately 36 Japanese subjects). This trial will be conducted at approximately 160 sites across 17 countries. Schematic

## Evobrutinib

### Phase IIb in Rheumatoid Arthritis MS200527-0060

presentations of the trial design are presented in [Figure 1](#). A detailed schedule of trial procedures/assessments is provided in [Table 1](#). Details of the study population are presented in [Table 2](#).

**Table 2** Trial Study Population

Diagnosis:	Moderate to severe RA
Methotrexate Therapy:	MTX-IR, on a stable dose of methotrexate
Prior exposure to bDMARD? (eg, TNF antagonists, IL-6 antagonists, anakinraa, abatacept, rituximab, etc.)	No prior exposure to approved or investigational bDMARD allowed.
Prior exposure to tsDMARD? (eg, JAK inhibitors, BTK inhibitors)	No prior treatment with investigational or approved tsDMARD(s) allowed.

bDMARD = biologic disease-modifying anti-rheumatic drug, BTK = Bruton's tyrosine kinase, IL = interleukin, JAK = Janus kinase, MTX-IR = inadequate response to methotrexate, RA = rheumatoid arthritis, TNF = tumor necrosis factor, tsDMARD = targeted synthetic disease-modifying anti-rheumatic drug.

a Not approved in Japan.

Approximately 50% of subjects will participate in a substudy using magnetic resonance imaging (MRI) to evaluate the ability of evobrutinib to prevent the progression of joint structural damage. These subjects will have hand and wrist MRI images and X-rays at the times indicated in the Schedule of Assessments ([Table 1](#)).

### Treatment Sequences

Eligible subjects will be randomly assigned in a 1:1:1:1 ratio to 1 of the 4 parallel treatment groups (N = 90/group), as detailed in [Table 3](#), in combination with their stable background MTX therapy. Subjects and Investigators will be blinded to the initial treatment assignment.

**Table 3** Treatment Groups and Regimens

Treatment Group	Regimen a,b
1	Evobrutinib 25 mg QD
2	Evobrutinib 75 mg QD
3	Evobrutinib 50 mg BID
4	Placebo

MTX = methotrexate.

a All subjects will continue to take their MTX background therapy along with trial treatment per treatment group.

b To maintain the study blind, all subjects will receive BID treatment. For subjects with QD treatment assignments, 1 dose a day will be study drug and 1 will be placebo.

## Evobrutinib

### Phase IIb in Rheumatoid Arthritis MS200527-0060

---

#### Trial Duration

Total duration of subject participation is approximately 5 months (approximately 20 weeks), which includes:

- Screening: 28 days (4 weeks)
- Treatment: 84 days (12 weeks)
- Safety Follow-up: 28 days (4 weeks).

The trial will be conducted on an outpatient basis. Subjects will attend clinic visits at regular intervals as indicated in the Schedule of Assessments (Table 1).

